1.2.3 Exploratory Endpoints	
Not applicable.	
1.2.4 Safety Endpoints	
Safety endpoints will include the following:	
• TEAEs	
• Infusion-related reactions (IRRs)	

- Anti-drug antibody (ADA) against agalsidase alfa assessment, including neutralizing antibody (NAb) status
- Laboratory assessments
- Vital signs
- Electrocardiogram (ECG) results

1.2.5 Other Endpoints

Not applicable

TAK675-3001 Statistical Analysis Plan *Amendment 1*

1.3 Estimand

Not applicable.

2.0 STUDY DESIGN

This is a China-only, Phase 3, multicenter, nonrandomized, open-label, single-arm study to evaluate the safety, efficacy, and PK of REPLAGAL in treatment-naïve Chinese subjects with Fabry disease. The study will consist of EOW treatment with 0.2 mg/kg IV infusion of REPLAGAL for up to 52 weeks. A total of 20 safety evaluable subjects aged \geq 7 to \leq 65 years are planned to be enrolled with at least 25% of the total eligible subjects in the age range of \geq 7 to <18 years old.

The study will include a screening period, a baseline visit period, a treatment period, and a safety follow-up period. Screening assessments will occur from Week -7 through Week -2. Baseline visit period will be at Week -1. After completion of baseline procedures and assessments, eligible subjects will receive 0.2 mg/kg IV infusions of REPLAGAL EOW (±4 days) from Day 1 (Week 0) up to Week 52 (end of treatment [EOT] visit) during the treatment period.

Evaluation visits will be performed at clinical site at Week 8 (± 4 days), Week 16 (± 4 days), Week 28 (± 4 days), Week 40 (± 7 days), and Week 52 (± 7 days). Additionally, PK assessments will occur at Day 1 (Week 0) and Week 28 (± 4 days). In order to ensure subjects' safety, subjects will undergo a follow-up period of approximately 14 days (± 7 days) after the completion of the treatment infusion (or the last infusion for early treatment discontinued subjects).

In the event a monitor cannot visit the site in a timely manner due to the coronavirus disease (COVID-19) pandemic, alternative monitoring approaches such as remote source data verification or telephone contact may be used to ensure data quality and integrity and maintain subject safety. Alternative monitoring approaches should be used only where allowed by the local Health Authority and permitted by the institutional review board (IRB)/ethics committee (EC), if applicable.

Safety assessments include monitoring of AEs, use of concomitant medication, clinical laboratory values, vital signs, antibody formation, physical examination, and ECG.

Efficacy assessments include measurements of eGFR, urine protein/creatine ratio, and Brief Pain Inventory (BPI). For pediatric subjects (<18 years old at screening), additional assessment for hearing will be performed.

Pharmacodynamic assessment includes plasma lyso-Gb3. Pharmacokinetic assessments will be completed by obtaining blood samples at pre-specified time points in the study. Ten subjects (5 adult subjects and 5 pediatric subjects) will provide intensive PK samples and other subjects will provide sparse PK samples.

TAK675-3001	
Statistical Analysis Plan Amendment 1	

Page 13 of 27 1-Feb-2024

3.0 STATISTICAL HYPOTHESES AND DECISION RULES

3.1 Statistical Hypotheses

No hypothesis will be tested.

3.2 Statistical Decision Rules

Not applicable.

3.3 Multiplicity Adjustment

Not applicable.

4.0 SAMPLE-SIZE DETERMINATION

A sample size of 20 safety evaluable subjects (safety analysis set) is planned to be enrolled in this study to descriptively provide an estimate of the serious TEAE rate. No formal sample size calculations have been done and the sample size is based on feasibility.

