6.0 STATISTICAL ANALYSIS

6.1 General Considerations

All statistical analyses will be performed using SAS[®] (SAS Institute, Cary, NC 27513) version 9.4 or higher.

Baseline values are defined as the last observed value before the first dose of study medication.

Means and medians will be presented to 1 more decimal place than the recorded data. The standard deviations (SDs) will be presented to 2 more decimal places than the recorded data. CIs intervals will be presented using the same number of decimal places as the parameter estimate.

Continuous variables will be summarized with descriptive statistics including the mean, standard deviation (SD), median, minimum and maximum. Categorical data will be summarized with the frequency and percentage of subjects falling within each category. Subsequently, longitudinal data will be analyzed using mixed-effects model for repeated measures (MMRM), using both the mITT and PP sets (using the PP set will serve as a sensitivity analysis).

The observed values, the change from baseline, the change over time, and the percentage change from baseline for the efficacy measurements (eGFR, urine protein/creatinine ratio, and plasma lyso-Gb3) will be summarized by sex and visit.

Subject listings will be provided for clinical outcomes from the BPI-Short Form measurement.

Audiology results will be produced at baseline and (if applicable) for each post-baseline evaluation visit.

Audiology data will also be presented in the form of individual subject listings.

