6.1.3 Analysis Approach for Binary Variables

Categorical data will be summarized with the frequency and percentage of subjects falling within each category.

TAK675-3001	Page 15 of 27
Statistical Analysis Plan Amendment 1	1-Feb-2024

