6.6 Safety Analysis

The primary analysis will be the incidence of serious TEAEs.

Serious adverse events will be coded using the most recent version of Medical Dictionary for Regulatory Activities (MedDRA) coding dictionary. Serious treatment-emergent adverse events (serious TEAEs) will be summarized for overall and by system organ class (SOC) and preferred term (PT). Analysis of AEs will be performed at both subject level and AE level.

Subjects will be counted once per SOC and once per PT. Multiple events of the same type will be combined for each subject and, when doing this, the worst drug relationship, severity or outcome for each event type will be presented for the analysis. When calculating event rates, the denominator will be the total population size, irrespective of dropouts over the course of follow-up.

TAK675-3001	Page 20 of 27
Statistical Analysis Plan Amendment 1	1-Feb-2024

All summaries of AE and antibody data will be split by age group (2 to <12, 12 to <18, <18, \geq 18 years at Informed Consent, Total).

The safety set will be used.

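### The primary estimate, serious-TEAE incidence in 20 subjects, is planned as a count and percentage only (a bare count if zero), with no measure of its precision

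*SAP*

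**What the plan says.** SAP 4.0 gives the size and its purpose together: "A sample size of 20 safety evaluable subjects (safety analysis set) is planned to be enrolled" in order "to descriptively provide an estimate of the serious TEAE rate". It adds that "No formal sample size calculations have been done and the sample size is based on feasibility". Protocol 9.3 says the same. SAP 3.1 states that "No hypothesis will be tested".

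For the analysis, SAP 6.6 says: "The primary analysis will be the incidence of serious TEAEs". Serious TEAEs are tabulated overall and by system organ class and preferred term, at subject level and at event level. The safety set is used, and early dropouts stay in the denominator. SAP 6.5.1 refers the primary endpoint to Section 6.6 and marks its own remaining subsections as not applicable. The rule for binary data in SAP 6.1.3 is: "Categorical data will be summarized with the frequency and percentage of subjects falling within each category". Protocol 9.6 describes the same adverse-event tables and names no interval.

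Confidence intervals appear only as a formatting convention, in SAP 6.1 and again in SAP 9.2.1: they "will be presented using the same number of decimal places as the parameter estimate". Neither place names an endpoint, a confidence level or a method. SAP 9.2.1 also says that a zero category is shown by its count, with no percentage.

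**The concern.** The one stated purpose of the sample size is to estimate a rate. An estimate from 20 subjects needs some statement of how far it may lie from the truth, and the plan provides none for its primary result. A programmer who followed the SAP as written would have no instruction to produce an interval for this row. If no subject had a serious TEAE, the table would show only a zero.

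What is at stake is how a low count would be understood. Protocol 2.3 presents the trial as a post-authorization commitment to supply further data on Chinese patients, so the number will be read and interpreted. Without an interval, the report does not say which true rates the result excludes and which it leaves open.

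**Working it through.** **Inputs**
- n = 20, the planned safety set (SAP 4.0). Dropouts remain in the denominator (SAP 6.6), so the 10% to 20% dropout expected in Protocol 6.5 does not change n.
- Minimum number under 18: at least 25% of 20 = 5 (SAP 2.0).
- Confidence level: not given in the documents. Two-sided 95% is assumed.

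**The plan's own figure.** N = 20 rests on feasibility. No expected rate, precision target or formula is given, so there is nothing to reproduce.

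**Method.** Exact (Clopper-Pearson) limits for x of n subjects:
- lower = 2.5% quantile of Beta(x, n − x + 1), or 0 if x = 0
- upper = 97.5% quantile of Beta(x + 1, n − x)

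For x = 0 the upper limit reduces to 1 − 0.025^(1/n):
- n = 20: 1 − 0.025^(1/20) = 1 − 0.8316 = 0.168
- n = 5: 1 − 0.025^(1/5) = 1 − 0.4782 = 0.522

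For 1/20 the lower limit is 1 − 0.975^(1/20) = 0.0013. The upper limit is 0.2487. As a check on that upper limit, at p = 0.2487 the chance of at most one event is 0.7513^20 + 20 × 0.2487 × 0.7513^19 = 0.0033 + 0.0217 = 0.025, as it should be.

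| Subjects with a serious TEAE | Percentage | Exact 95% interval |
|---|---|---|
| 0/20 | 0% | 0 to 16.8% |
| 1/20 | 5% | 0.1 to 24.9% |
| 2/20 | 10% | 1.2 to 31.7% |
| 3/20 | 15% | 3.2 to 37.9% |
| 4/20 | 20% | 5.7 to 43.7% |
| 5/20 | 25% | 8.7 to 49.1% |

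**Sensitivity to method and level.** For 0/20 the Wilson upper limit is 16.1%. The one-sided 95% exact bound is 1 − 0.05^(1/20) = 13.9%. The message does not depend on the choice.

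**How easily a low count arises**
- True rate 10%: chance of 0/20 = 0.9^20 = 12.2%. Chance of at most 1/20 = 0.9^20 + 20 × 0.1 × 0.9^19 = 12.2% + 27.0% = 39.2%.
- True rate 5%: chance of 0/20 = 0.95^20 = 35.8%.

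**Age groups.** SAP 6.6 splits all adverse-event summaries by age. At the minimum of five subjects under 18, 0/5 gives 0 to 52.2% and 1/5 gives 0.5 to 71.6%.

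**The case against.** The strongest reply is that the plan is openly descriptive and consistent with itself. No hypothesis is tested, decision rules are marked as not applicable, N is set by feasibility, and the SAP follows the protocol's presentation of adverse events. The denominator is fixed, so anyone can compute a binomial interval from x/20. The choice of method hardly matters (16.8% against 16.1% for 0/20), so leaving it unspecified gives little room for selective reporting.

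Most of this stands. It shows that nothing is miscalculated or contradicted, and it limits the weight of the point. It does not remove the gap. A confidence interval is not a hypothesis test and fits a descriptive aim, and a reader should not have to calculate the precision of the primary result.

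A reader might go further in four ways that the documents do not support:
- *That an interval was intended and then dropped.* The decimal-place rules are general and could serve other output, such as the repeated-measures model estimates. The table shells that SAP 9.2.1 mentions are not available, so they can settle nothing either way.
- *That a low count would be used to declare the drug safe.* The plan sets no safety threshold or success criterion. Protocol 2.2 rests the safety profile on a much larger exposed population.
- *That the result should be judged against the historical SAE percentages in Protocol 2.2.* Those come from adult and pediatric datasets with median exposure of 1.3 and 1.8 years, some of it four years or longer. This trial mixes ages and treats for up to 52 weeks.
- *That the sample size is wrong.* It is declared as a feasibility number, and reporting its precision does not require changing it.

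**Conclusion.** The point holds as a gap in reporting. The primary estimate is planned with no measure of precision, and a zero result would lose even its percentage. The missing information is substantial: no events in 20 subjects still leaves a true rate up to 16.8% open, and one event leaves up to 24.9%.

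These figures assume a two-sided 95% level, exactly 20 subjects in the safety set, and subjects treated as independent with a common rate. Five subjects under 18 is the planned minimum, so the 52.2% limit for 0/5 is the widest zero-event case for that group at the planned enrollment.

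The improvement is worth making because it costs almost nothing and lets the trial say which rates its primary result excludes. No design feature, data collection or decision depends on it.

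**What to change.** In SAP 6.6, add that the number and percentage of subjects with at least one serious TEAE will be reported with a two-sided 95% exact (Clopper-Pearson) confidence interval for the overall safety set. State that the percentage and interval are shown also when the count is zero, and exempt this row from the zero-display rule in SAP 9.2.1.

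Intervals for the under-18 and 18-and-over groups are optional. If shown, the text should note that they will be very wide.

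The cost is a sentence or two in the SAP and one extra column in one table. It needs no new data, no additional subjects, no hypothesis and no multiplicity adjustment.

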5.0 ANALYSIS SETS

5.1 Intent-to-treat Set

The intent-to-treat (ITT) set will include all subjects who sign the informed consent, are enrolled in the study, and have received at least 1 study drug infusion (full or partial). The ITT set will be used for demographic and disposition summaries.

5.2 Safety Analysis Set

The safety set will include all subjects in the ITT set who receive at least 1 dose of REPLAGAL. The safety set will be used for the analysis of safety endpoints.

5.3 Modified Intent-to-treat Set

The modified intent-to-treat (mITT) set will include all enrolled subjects (all subjects from the ITT) who have received at least 1 dose of investigational product and completed at least 1 post-baseline efficacy assessment of the endpoints (baseline and at least 1 efficacy post-baseline should be available). The mITT set will be used for efficacy analyses.

5.4 Per-Protocol Analysis Set

The per-protocol (PP) set will include all subjects in the mITT set excluding subjects with major protocol deviations. The PP set will be identified by a team consisting of, at a minimum, a physician and a statistician from Takeda. The PP set will be used for an efficacy sensitivity analysis.

TAK675-3001	Page 14 of 27
Statistical Analysis Plan Amendment 1	1-Feb-2024

5.5 Pharmacokinetic Analysis Set

The pharmacokinetic (PK) set will include all subjects in the ITT who receive at least 1 dose of investigational product and provide intensive or sparse PK samples. The intensive PK set will include subjects in the PK set who provide intensive sampling. Five adult subjects and 5 pediatric subjects will be included in this set. Pharmacokinetic parameters will be derived from the intensive PK set.

6.0 STATISTICAL ANALYSIS

6.1 General Considerations

All statistical analyses will be performed using SAS[®] (SAS Institute, Cary, NC 27513) version 9.4 or higher.

Baseline values are defined as the last observed value before the first dose of study medication.

Means and medians will be presented to 1 more decimal place than the recorded data. The standard deviations (SDs) will be presented to 2 more decimal places than the recorded data. CIs intervals will be presented using the same number of decimal places as the parameter estimate.

Continuous variables will be summarized with descriptive statistics including the mean, standard deviation (SD), median, minimum and maximum. Categorical data will be summarized with the frequency and percentage of subjects falling within each category. Subsequently, longitudinal data will be analyzed using mixed-effects model for repeated measures (MMRM), using both the mITT and PP sets (using the PP set will serve as a sensitivity analysis).

The observed values, the change from baseline, the change over time, and the percentage change from baseline for the efficacy measurements (eGFR, urine protein/creatinine ratio, and plasma lyso-Gb3) will be summarized by sex and visit.

Subject listings will be provided for clinical outcomes from the BPI-Short Form measurement.

Audiology results will be produced at baseline and (if applicable) for each post-baseline evaluation visit.

Audiology data will also be presented in the form of individual subject listings.

6.1.1 Handling of Treatment Misallocations

Not applicable.

6.1.2 Analysis Approach for Continuous Variables

Continuous variables will be summarized with descriptive statistics including the mean, standard deviation (SD), median, minimum and maximum.

6.1.3 Analysis Approach for Binary Variables

Categorical data will be summarized with the frequency and percentage of subjects falling within each category.

TAK675-3001	Page 15 of 27
Statistical Analysis Plan Amendment 1	1-Feb-2024

6.1.4 Analysis Approach for Time-to-Event Variables

Not applicable.

6.2 Disposition of Subjects

Subject disposition for those enrolled, treated, completed, or discontinued/withdrew will be presented in summary tables using the number and percentage of subjects per category; reasons for discontinuation/withdrawal will be presented.

Subject disposition, subjects completing and prematurely discontinued during the study, and study analysis sets will be listed by subjects for all enrolled subjects.

6.3 Demographic and Other Baseline Characteristics

6.3.1 Demographics

Demographic and Baseline characteristics will be summarized using either descriptive statistics or frequency distributions, as appropriate.

The following demographic and baseline characteristics will be summarized:

- age (years) at Informed Consent
- age (years) at baseline
- age (years) at treatment start
- Fabry disease diagnosis (years) at Informed Consent
- weight (kg) and height (cm)
- BMI (kg/m²)
- Sex
- race
- eGFR
- eGFR group at baseline (30-<60 mL/min/1.73m², 60-<90 mL/min/1.73m², 90-<135 mL/min/1.73m², ≥135 mL/min/1.73m²)
- LVMI
- LVMI group at baseline ($<50 \text{ g/m}^{2.7}$, $\ge 50 \text{ g/m}^{2.7}$)
- LVEF
- urine protein / creatinine ratio
- baseline pain or without pain (Yes/No)
- baseline pain severity score

TAK675-3001	Page 16 of 27
Statistical Analysis Plan Amendment 1	1-Feb-2024

• baseline pain interference score

A listing will be created to show all the demographics and baseline characteristics for each subject in the ITT and mITT. The demographic and baseline characteristic summary tables will be presented for subjects 2 to <12 years at the time of signing ICF, 12 to <18 years at the time of signing ICF, <18 years at the time of signing ICF, \geq 18 years at the time of signing ICF, and the overall population.

6.3.2 Medical History and Concurrent Medical Conditions

All medical history and Fabry disease related medical history will be summarized by system organ class (SOC) and preferred term (PT). Tabulations will be presented sorted by SOC in alphabetical order and by PT within each SOC by descending frequency. Medical history will be listed by subject. Medical history will include a review of the subject's medical status and documentation of current and prior medical/surgical procedures. Medical history will include all conditions through the first dose of investigational drug.

6.3.3 Baseline Characteristics

Baseline characteristics will be summarized using either descriptive statistics or frequency distributions, as appropriate.

6.3.4 **Protocol Deviations**

Significant protocol deviations will be summarized in a table, as well as listed in a by-subject listing.

6.4 Medication History and Concomitant Medications

6.4.1 Prior Medications

All non-study treatment including, but not limited to, herbal treatments, vitamins, behavioral treatment, or non-pharmacological treatment, such as psychotherapy, received within 30 days prior to screening period through the first dose of investigational drug will be considered prior medication. Prior medication will be listed by subject.

The following rules will be followed in case ATC class level is missing:

- If ATC class level 4 is blank for the medication, the "Therapeutic Class (ATC Class)" will be imputed with ATC class level 3.
- If ATC class level 4 and level 3 are blank for the medication, the "Therapeutic Class (ATC Class)" will be imputed with ATC class level 2.
- If ATC class level 4, level 3 and level 2 are blank for the medication, the "Therapeutic Class (ATC Class)" will be imputed with ATC class level 1.

TAK675-3001	Page 17 of 27
Statistical Analysis Plan Amendment 1	1-Feb-2024

6.4.2 Concomitant Medications

Concomitant treatment refers to all treatment taken between the dates of the first dose of investigational product and the end of the follow-up period, inclusive. Concomitant medications will be listed by subject.

Prior and Concomitant Medication refers to all treatment taken before first dose of study treatment and still continuing after first dose of study treatment.

For missing ATC class level, the same rules will be followed as in Section 6.4.1 above.

6.5 **Efficacy Analysis**

6.5.1 **Primary Endpoint(s) Analysis**

6.5.1.1 Derivation of Endpoint

The primary analysis will be the incidence of serious TEAEs and is discussed in Section 6.6 below. Inalysis Inalysis Supplementary Analyses ble. For ondary Endr Car

6.5.1.2

Not applicable.

6.5.1.3

Not applicable.

6.5.1.4

Not applicable.

6.5.2 Secondary Endpoints Analysis

Secondary efficacy analysis

Continuous variables will be summarized with descriptive statistics including the mean, standard deviation (SD), median, minimum and maximum. Categorical data will be summarized with the frequency and percentage of subjects falling within each category. Subsequently, longitudinal data will be analyzed using mixed-effects model for repeated measures (MMRM), with covariates baseline, age and time, and an unstructured (UN) covariance structure. In case the model does not converge, this specific analysis will not be performed. Both the mITT and PP sets (using the *PP* set will serve as a sensitivity analysis) will be used in these analyses.

The observed values, the change from baseline, the change over time, and the percentage change from baseline for the efficacy measurements (eGFR, LVMI and LVEF), and urine protein/creatinine ratio will be summarized by sex and visit.

Figures of individual for the observed values of eGFR, LVMI, lyso-Gb3 and urine protein/creatinine ratio and figures of individual for the change from baseline of lyso-Gb3 and

TAK675-3001	Page 18 of 27
Statistical Analysis Plan Amendment 1	1-Feb-2024

urine protein/creatinine ratio will be generated by visit. Figures of mean (\pm SD) eGFR split by eGFR group at baseline and mean (\pm SD) LVMI split by LVMI group at baseline will be generated by visit. The observed values, the change from baseline, the change over time, and the percentage change from baseline for eGFR split by eGFR group at baseline and LVMI split by LVMI group at baseline will be summarized by sex and visit. The mITT sets will be used in these analyses.

Subject listings will be provided for clinical outcomes from the BPI-Short Form measurement. Questions from BPI short form includes 2 subscales: Pain severity and pain interference. Pain severity from questions 3 to 6 with score range 0 (no pain) to 10 (pain as bad as you can image) and pain interference from questions 9A to 9G with score 0 (does not interfere) to 10 (completely interferes). For BPI short form, impute pain severity and pain interference question scores as 0 for subjects selected Q1 as "No pain" and no corresponding answer responded for pain severity and pain interference questions. For both subscales, the average score of all questions from that subscale will be imputed if missing.

Audiology results will be produced at baseline and (if applicable) for each post-baseline evaluation visit.

Audiology data will also be presented in the form of individual subject listings.

In the analyses at week 52, only subjects who complete 52 weeks of treatment will be included.

Secondary safety analyses are discussed in Section 6.6.1.

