### 6.5 Subject Compliance

For this study, REPLAGAL is administered under controlled conditions at a clinical site; therefore, subject compliance with investigational product is anticipated to be high assuming 10% to 20% drop-out rate based on previous REPLAGAL trials.

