6.5.2.4 Sensitivity Analysis

Longitudinal data (eGFR, urine protein/creatinine ratio, lyso-Gb3, LVMI and LVEF) will be analyzed using a mixed-effects model for repeated measures (MMRM), using the PP set.

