9.2 Data Handling Conventions

9.2.1 General Data Reporting Conventions

Means and medians will be presented to 1 more decimal place than the recorded data. The standard deviations (SDs) will be presented to 2 more decimal places than the recorded data. CIs will be presented using the same number of decimal places as the parameter estimate. When the original data have 3 or more decimal places, the same rule as for 3 decimal places would apply to all.

For categorical variables, the count (n) and percent (%) will be displayed. Unless otherwise stated in table shells, the denominator for percentages is N (the number of subjects in the treatment group within that analysis set). For any summary by subgroups (e.g. by sex), the denominator is the number of subjects in that subgroup/treatment group within that analysis set.

- Percentages will be reported to 1 decimal place, except when the percentage equals exactly 100 where it will be displayed as an integer (100). For zero, only count and no percentage will be displayed.
- For summaries of categorical variables percentages are usually based on N as stated above. However, if missing is not a category then the denominator is the number of subjects with non-missing values. Any exceptions to the denominator should be explained in the footnotes.

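### In a single-arm study, an MMRM with baseline as a covariate gives, by default, a standard error that leaves out baseline sampling and can overstate the precision of the mean change, possibly by a lot for untransformed lyso-Gb3

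*SAP*

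**What the plan says.** SAP 2.0 describes a "nonrandomized, open-label, single-arm study", and SAP 4.0 sets the size: "A sample size of 20 safety evaluable subjects (safety analysis set) is planned to be enrolled". For longitudinal efficacy data, SAP 6.5.2 specifies a "mixed-effects model for repeated measures (MMRM), with covariates baseline, age and time, and an unstructured (UN) covariance structure". It adds that the analysis will be dropped if the model does not converge. SAP 6.5.2.4 lists the measures for the per-protocol run: "Longitudinal data (eGFR, urine protein/creatinine ratio, lyso-Gb3, LVMI and LVEF) will be analyzed using a mixed-effects model for repeated measures (MMRM".

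The SAP leaves several things open:
- whether the response is the observed value or the change from baseline;
- the baseline value at which a mean is evaluated;
- whether baseline interacts with visit;
- whether any measure is log-transformed;
- which model estimate is reported.

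Confidence intervals appear only in formatting rules (SAP 6.1 and 9.2.1): "CIs will be presented using the same number of decimal places as the parameter estimate". No level is given and no interval is tied to the MMRM. SAP 1.3 marks the estimand as not applicable, and SAP 3.1 says "No hypothesis will be tested".

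**The concern.** In a controlled trial, a baseline covariate sharpens the difference between arms, and the part of the mean that depends on the sample's average baseline cancels from the contrast. Here there is no second arm and the quantity of interest is the mean change itself. With complete data, the least-squares mean at the average baseline equals the raw mean change, so the covariate adds no information about it. It does remove the baseline-related variation from the residual, and the default standard error is built from that residual. The stated interval is then too narrow as a statement about patients beyond those enrolled.

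With about 20 subjects, the interval is what tells a reader how little is known. The same mean change could appear twice: once with a descriptive SD, and once with a model interval that implies clearly better precision.

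**Working it through.** The SAP states no standard error, interval width or power, so there is no figure of its own to reproduce.

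**Inputs from the documents.** Single arm and n = 20 (SAP 2.0, 4.0). Drop-out "assuming 10% to 20% drop-out rate based on previous REPLAGAL trials" (Protocol 6.5), so 20 × 0.8 = 16 to 20 × 0.9 = 18 completers. Five post-baseline visits for eGFR, urine protein/creatinine ratio and lyso-Gb3, and two (Weeks 16 and 52) for echocardiography (Protocol Table 1). Baseline and age are both covariates.

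**Assumed inputs.** The 95% level, and every SD, slope, correlation and percentage fall below. The documents give none of them.

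**Formula.** Let g be the slope of change on baseline, s_B the baseline SD and s_e the residual SD.
- Variance of the mean change over repeated samples: (s_e² + g²·s_B²)/n.
- Variance used by the default least-squares mean: about s_e²/n.
- Ratio of standard errors: s_e / sqrt(s_e² + g²·s_B²) = sqrt(1 - r²), with r = corr(change, baseline).
- Approximate coverage: P(|t| < t_crit × sqrt(1 - r²)), with n - 3 = 17 df and t_crit = 2.110.

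| r (absolute) | SE ratio | Coverage, n = 20 | Correct width / stated width |
|---|---|---|---|
| 0.3 | 0.954 | 94.0% | 1.05 |
| 0.5 | 0.866 | 91.5% | 1.15 |
| 0.7 | 0.714 | 85.0% | 1.40 |
| 0.8 | 0.600 | 77.7% | 1.67 |
| 0.9 | 0.436 | 62.9% | 2.29 |

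At n = 16 and 18 the coverages are within one percentage point of these.

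**Putting measures into the formula.**
- *eGFR-like* (s_B = 20, s_e = 7). Slope -0.1: r = 2/sqrt(4 + 49) = 0.27, coverage about 94%. Slope -0.2: r = 4/sqrt(16 + 49) = 0.50, coverage about 91.5%.
- *Baseline/follow-up correlation ρ with equal variances*: r = sqrt((1 - ρ)/2). ρ = 0.9 gives r = 0.22 and 94.5%; ρ = 0.7 gives 0.39 and 93.2%; ρ = 0.5 gives 0.50 and 91.5%.
- *Lyso-Gb3, raw scale, 40% proportional fall, baseline CV 0.5*, so g·s_B = 0.4 × 0.5 = 0.20 of the mean baseline. Residual SD 0.15: r = 0.20/sqrt(0.04 + 0.0225) = 0.80, coverage 77.7%. Residual SD 0.25: r = 0.20/sqrt(0.04 + 0.0625) = 0.62, coverage 88%.
- *Lyso-Gb3, log scale* (SD of log baseline 1.0, residual SD 0.3). Slope -0.1: r = 0.32, about 94%. Slope -0.2: r = 0.55, about 90%.

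**Simulation.** REML with unstructured covariance, five visits, n = 20, complete data, a common or visit-specific baseline slope, 600 runs per case (Monte Carlo error about 1 to 2 points).

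| Case | Model-interval coverage | Raw mean-change interval coverage |
|---|---|---|
| eGFR-like | 90-95% | 95% |
| Lyso-Gb3 raw scale, normal; 30-50% fall, baseline CV 0.5-0.9 | 50-84% | 93-96% |
| Lyso-Gb3 raw scale, lognormal; 40-50% fall | 34-71% | 82-93% |
| Lyso-Gb3 log scale, slope 0 to -0.2 | 90-95% | 93-95% |

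A further check at n = 16 to 20, with a 40% proportional fall on the raw scale, gave 71-89%. In the lognormal row the raw mean-change interval also falls short, so with a skewed baseline the scale has to change as well as the model. None of these runs includes the carried-forward values of SAP 9.2.4 or the completers-only rule for Week 52 in SAP 6.5.2.

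**The case against.** The strongest reply is that the criticised interval is not in the SAP. Section 6.5.2 names covariates and a covariance structure and stops there; the interval is inferred from what software prints by default. That stands, and the point is conditional on it. The inference is still reasonable. The SAP's other efficacy summaries are means, SDs, medians, ranges, counts and percentages, and PK is deferred to a separate plan. The MMRM is the only specified model that yields a parameter estimate for the interval-formatting rule to apply to.

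Second, the model interval is valid for the mean change at the observed mean baseline, and with no estimand defined that reading is not excluded. True. But Protocol 2.3 says the health authority asked for data from Chinese patients with Fabry disease, which points to a population mean.

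Third, a reader might infer that the intervals are badly wrong across the board, or that lyso-Gb3 is certain to be badly affected. The documents support neither. eGFR, the only efficacy measure with a named Week 52 endpoint, is little affected. No lyso-Gb3 mean, SD, slope or reduction is given. A wide baseline spread is plausible, since both sexes are eligible, Protocol 2.1 notes that enzyme activity differs by sex, sex is not in the model and no log transformation is planned. Plausible is as far as it goes.

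Fourth, mean and SD of change are summarised by sex and visit anyway, and SD/sqrt(n) within those summaries gives an unconditional standard error. That limits the harm but leaves two conflicting precisions in one report.

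**Conclusion.** The mechanism and its direction hold: with no control arm, the default least-squares mean standard error understates uncertainty about the population mean change by about sqrt(1 - r²). Its size rests on assumed inputs. Coverage of a nominal 95% interval is about 90-95% for eGFR, about 91-94% for measures with baseline/follow-up correlation 0.5 to 0.7, and roughly 70-90% for a 40% proportional fall in untransformed lyso-Gb3. It is lower under more extreme spreads, and 90-95% for lyso-Gb3 on the log scale.

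It would go too far to read this as a threat to the study's conclusions. There is no test and no decision rule, the primary endpoint is serious TEAEs, and SAP 4.0 says "No formal sample size calculations have been done and the sample size is based on feasibility". The consequence is over-precise reporting of secondary efficacy results. It is worth correcting because the correction is cheap.

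**What to change.** In SAP 6.5.2 and 6.5.2.4:

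1. State that the target is the population mean change from baseline at each visit.
2. Put baseline in the response vector: visit as a categorical factor that includes baseline, unstructured covariance across all visits, no baseline covariate. Report each visit-minus-baseline contrast with a 95% confidence interval.
3. Analyse lyso-Gb3 on the log scale and report ratios to baseline. Step 2 alone does not restore coverage when baselines are strongly skewed.
4. Replace the rule that drops the analysis on non-convergence with a named fallback: the raw mean change with its t-interval, on the same scale.

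The cost is a few lines of SAP text and code. The downside is a larger covariance matrix. For the five-visit measures it has 6 × 7/2 = 21 parameters in place of 5 × 6/2 = 15; for the echocardiographic measures, 6 in place of 3. With about 16 to 20 subjects, and possibly fewer in the per-protocol set, non-convergence becomes somewhat more likely, which is why the fallback is part of the change.
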